The high-risk youth who will be enrolled in the proposed study live in a predominantly rural, low socioeconomic region of Oklahoma. They currently have access to several well-equipped fitness centers in the region, but these resources are underutilized. Although it is well-accepted that regular exercise can improve individual health and reduce the socioeconomic burden of diabetes, reducing barriers and effectively modifying behavior presents a significant challenge. Prior studies have shown that paying adults for desired behaviors and/or health outcomes can be effective, but the use of financial incentives to shape exercise behavior in adolescents has not been reported. We hypothesize that monetary incentives will encourage obese, insulin resistant American Indian youth to establish and maintain better exercise habits, ultimately resulting in better health. We propose to provide transportation for participants to the wellness centers and individually tailored instruction and oversight by fitness professionals so that the centers are accessible and appealing. The provision of monetary incentives is designed to reinforce the frequency and duration of exercise. Our strategy to accomplish these goals is outlined in the following Specific Aims:

Aim 1: To determine whether financial incentives will increase the frequency of exercise sessions performed by American Indian youth at a community fitness center. Obese, insulin resistant American Indian adolescents will be randomly assigned to one of two groups for a 16-week exercise program: Control (\$4/session, up to 3 sessions/week, provided as compensation for time), or Incentive (\$4, \$10, and \$16 for the first, second, and third session each week, respectively). All participants will be provided transportation to and from the fitness center and professional instruction and supervision for aerobic exercise training, but will differ only in the amount of money they are eligible to collect for their attendance. A secondary goal of this Aim is to assess the association between exercise frequency and changes in diabetes-related risk factors, including insulin sensitivity, body composition, and blood lipids.

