Design: Specific Aims 1-3 will follow a single prospective, randomized trial design, with 105 participants

enrolled and 80-90 entering the exercise program (**Fig 1**). The individual Aims are distinguished by sequential study phases and varying incentive structures (**Fig 2 and 3**). Aim 4 is a cross-sectional comparison between overweight/obese participants entering the main trial and two groups of normal weight youth (up to 40 participants per group) with either low physical activity and fitness or high physical activity and fitness (up to 40 participants per group).

Participants: Male and female American Indian youth 11-21 years old will be recruited from the Choctaw Health Service Area of SE Oklahoma. For the primary exercise incentives study, the eligibility criteria include BMI ≥85th percentile for age- and sexspecific norms based on growth charts from the Centers for Disease Control, maturation level ≥Tanner Stage 2 for breasts (girls) or genitalia (boys), family history of T2D, and recent history of low physical activity. Low physical activity, defined as attaining < 30 minutes of structured moderate-to-vigorous intensity exercise on \leq 3 days/week over the preceding 3 months, will be confirmed through guestionnaires and objective monitoring as described below. For both normal weight comparison groups in Aim 4, eligibility will include BMI greater than 20th and less than 85th percentile, maturation level ≥Tanner Stage 2 for breasts (girls) or genitalia (boys), and recent history of either a) low physical activity (same as the overweight/obese group) or, b) high physical activity (>30 minutes of structured moderate-to-vigorous intensity exercise on >3 days/week over the preceding 3 months. T2D family history will be recorded but will not be an inclusion criterion for the normal weight groups. Fitness level and physical activity will be determined through testing, described below. Additional enrollment and retention eligibility criteria are: lack of diabetes or other potentially confounding metabolic disorders, able to safely exercise, willingness to complete the testing and participation schedule, and not on medications known to impact the stated outcomes. A medical history and physical exam will be performed to assure suitability for the study during the initial screening.

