Exercise training: The 16-week Aim 1 exercise training period will begin within two weeks after the Pretest. Training sessions will be performed at one of the Wellness Centers described in Facilities, with potential for additional sites depending on needs and the availability of appropriate supervision. All participants already have free membership to the Wellness Centers as a benefit provided to Certificate Degree of Indian Blood (CDIB) cardholders. Free transportation will be arranged through a shuttle service already in place for medical visits. Fitness professionals at each center will provide instruction, supervision, and ongoing guidance to assure that exercise sessions are completed safely and effectively. Participants and their parent/guardian will be instructed that the exercise goal throughout the entire 48-week study is to achieve 60 min/day of moderateto-vigorous physical activity (MVPA), consistent with current guidelines for children (13, 31, 90). MVPA is defined as continuous exercise that elicits a heart rate \geq 70% of peak heart rate. Each participant will be able to choose the frequency of visits to the wellness center and the length of time engaged in MVPA, since the purpose of the study is to test the effect of incentives on exercise behavior. Several types of exercise can be selected, including walking, running, cycling, stair stepping, aerobic dance or other activities. Instructors will advise a gradual increase in exercise intensity and duration as tolerated over the first 2-3 weeks to allow for familiarization and safety. To promote healthy behavior within the community and foster social support, all participants will be invited to exercise with family members or friends if they choose and this will be recorded as a covariate. As in our previous studies, exercise intensity will be monitored by recording heart rate with a chest strap transmitter that outputs to a computer for quantification and data storage. These data will be used to document training sessions. To provide backup in the event of technical failure, training sessions will also be recorded in an exercise log by each participant and confirmed by fitness center staff. Exercise will be quantified by frequency (sessions per week), duration (length of sessions), and total volume (Metabolic Equivalent of Task-hours, MET-h, a measure of intensity relative to resting x activity time).

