Group assignment: Within each Aim, participants will be assigned to one of two groups using a randomized stratified block design that was selected to reduce the potential for baseline variability among the groups. Participants will be assigned to blocks of 2 (duos) matched for age and sex. A participant who is not yet matched on the two factors will determine the age and sex for a newly established duo. The next participant to meet those matching criteria will be assigned to that duo. Each duo will have one participant in each of the intervention groups, but the group to which each participant in a block is assigned will be pre-determined by a unique random permutation.

Incentive programs

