Data analyses: Since group assignments will be balanced for age and sex, the groups are expected to be similar at baseline. Additional comparisons will be performed to identify demographic or other variables on which the groups might differ (e.g., weight loss) that could affect the primary outcomes. Subsequent analyses will adjust for these potentially confounding variables. Regression models, which adjust for modifier (or confounding) variables identified in initial data exploration, will compare between-group differences in the primary outcomes. Since we anticipate that the number of fitness center visits, which is the primary outcome in Aim 1, will follow a Poisson distribution typical of counts, we will explore a multivariable Poisson regression model to analyze that aim. To assess Aim 2, a more conventional regression model will analyze the primary outcome, which is the total time that participants engage in exercise. The effects of exercise training on secondary outcomes will be analyzed similarly, using multiple linear regression. Analysis of Aim 3 will also utilize multivariate modeling to determine which factors, including exercise group assignment, best explain the change in exercise volume and clinical outcomes over the final phase of the study. Residuals generated from regression models will be inspected for normality and data will be log-transformed or subjected to nonparametric testing as appropriate. Aim 4 is a cross-sectional study design so the main effects of physical activity (high versus low), fitness (high versus low) and body size (normal weight versus overweight/obese) on biomarkers of metabolic disease risk will be initially determined using an analysis of variance approach, with Bonferroni tests to make pairwise comparisons between groups. A multivariate modeling approach, similar to that used in Aims 1-3, will be used to identify the best sets of predictor variables for specific biomarkers. A P value <0.05 will be considered statistically significant.

BIBLIOGRAPHY

- 2. Adams SH. Emerging perspectives on essential amino acid metabolism in obesity and the insulinresistant state. *Adv Nutr* 2: 445-456, 2011.

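### Covariates for the between-arm models are chosen after data exploration, so the matching factors age and sex, and training center, have no assured place in them

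*Combined protocol and SAP*

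**What the plan says.** **Allocation.** The Group assignment section applies the same scheme in each of Aims 1 to 3: "Participants will be assigned to blocks of 2 (duos) matched for age and sex". It adds: "Each duo will have one participant in each of the intervention groups". Center is not a matching factor.

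**Where the outcomes arise.** Specific Aims says of the target youth: "They currently have access to several well-equipped fitness centers in the region, but these resources are underutilized". The Exercise training section says: "Training sessions will be performed at one of the Wellness Centers described in Facilities, with potential for additional sites depending on needs". Staffing is local to the site: "Fitness professionals at each center will provide instruction, supervision, and ongoing guidance". Membership is free for everyone, and on transport the plan says: "Free transportation will be arranged through a shuttle service already in place for medical visits".

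**Analysis.** The Data analyses section expects similar groups at baseline because allocation is balanced for age and sex. It then plans comparisons to find variables on which the groups differ. The model rule reads: "Regression models, which adjust for modifier (or confounding) variables identified in initial data exploration". Aim 1 visits are to be explored with a multivariable Poisson model, Aim 2 time with conventional regression, and Aim 3 with multivariate modeling of the factors that best explain change. None of these passages names age, sex or center as a fixed term, and none mentions overdispersion or robust standard errors. The only covariate named in advance in the Exercise training section is exercising with family or friends.

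**The concern.** Factors used to restrict randomization belong in the model. Matching makes the two arms alike on age and sex, so the true sampling variance of the arm difference falls. A model without those factors leaves their variance in the residual and reports a standard error that is too large.

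Center is a different case. It is not balanced by design, but it is a plausible predictor of how often and how long a participant trains, because the primary outcomes of Aims 1 and 2 are produced there.

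Choosing covariates after exploration adds a further problem: two analysts with the same data could settle on different models and report different incentive effects. With 80–90 participants entering the exercise program, the choice can matter for a result near P = 0.05.

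**Working it through.** The plan gives no power calculation, variance, attendance rate or number of centers, so it has no figure to reproduce. The sizes below are illustrations.

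**Inputs.** From the Design paragraph: 80–90 participants enter the exercise program; I take N = 86, that is 43 duos. From Data analyses: alpha 0.05, assumed two-sided. Assumed: K = 3–5 equal centers; 5–20% of outcome variance explained by center, or by age and sex; a mean of 24 visits, half of the 48 targeted.

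**1. Age and sex.** Suppose matching is exact and age and sex explain a share R² of variance. In units of the true standard error, the unadjusted test needs 1.96/√(1−R²) to reject, while the adjusted test needs 1.96. If the unadjusted test has 80% power, the true standardized effect is 1.96/√(1−R²) + 0.842, and adjusted power is Φ(that value − 1.96).
- R² = 0.05: 2.011 + 0.842 − 1.96 = 0.893, power 81.4%
- R² = 0.10: 2.066 + 0.842 − 1.96 = 0.948, power 82.8%
- R² = 0.20: 2.191 + 0.842 − 1.96 = 1.073, power 85.8%

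The gain is about 1–6 points.

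**2. Center: precision.** Let ρ be the intraclass correlation for center. With allocation not stratified by center, estimating K centers costs on average (K−1)/N of the information. The gain in precision is

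G = (1 − (K−1)/N) × [1 − ρ + ρ(K−1)/K]/(1−ρ) − 1.

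For K = 3 and ρ = 0.10: (84/86) × (0.9667/0.90) − 1 = 0.9767 × 1.0741 − 1 = +4.9%.

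| ρ | K = 3 | K = 4 | K = 5 |
|---|---|---|---|
| 0 | −2.3% | −3.5% | −4.7% |
| 0.05 | +1.1% | +0.3% | −0.6% |
| 0.10 | +4.9% | +4.6% | +3.8% |
| 0.20 | +14.0% | +14.6% | +14.4% |

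If ρ is instead the share actually realized among the trial's centers, G = (1 − (K−1)/N)/(1−ρ) − 1. For K = 3 that gives +2.8%, +8.5% and +22.1% at 5%, 10% and 20%; for K = 5 it gives +0.4%, +5.9% and +19.2%. Simulation gave about −3% to −2%, 0–3%, 4–8% and 12–18% at 0, 5%, 10% and 20%. This agrees with the formulas to within about two points, apart from the realized-share reading at 20%, where the formula runs up to 22%.

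**3. Center: Aim 1 standard error.** With Poisson variation within centers and between-center coefficient of variation c, the variance of the arm difference exceeds the Poisson value by a factor of about 1 + mean × c² × (K−1)/K. For mean 24, c = 0.1 and K = 4 this is 1 + 0.24 × 0.75 = 1.18. The critical value is then effectively 1.96/√1.18 = 1.80, and the type I error is about 7%. Simulation with 42 per arm and 3–5 centers gave 0.07, 0.12–0.13 and 0.18–0.21 for c = 0.1, 0.2 and 0.3; robust standard errors held it near 0.05. The larger values of c are strong assumptions. At mean 24, c = 0.1 already makes center 5.76/(5.76 + 24) = 19% of the variance, and c = 0.2 makes it 49%. Within the 5–20% range of step 2, the inflation from center alone stays at about 7% or below.

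**4. Matching on center instead.** With whole-year ages 11–21, two sexes and equal cells (22 cells), about 11 of 80–90 participants are expected to be unmatched. Adding 3–5 centers raises this to about 30–44.

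**The case against.** The strongest reply is that the plan's covariate rule is open, not closed. It admits modifiers as well as confounders, and a modifier need not differ between arms. The Aim 3 wording would also let center in as a predictor. A reader might infer that center will be dropped whenever it looks balanced; the text does not say so. It supports only that center is not pre-specified. That part of the reply stands, but admission after exploration does not replace a term fixed beforehand.

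A reader might also infer that an uneven arm split within a center biases the incentive effect. Individuals are randomized, so such splits are ordinary chance error. They are the same variance already counted as lost precision, not a second harm. With 86 participants the standard error is 2/√86 = 0.22 SD. If center explains 10–20% of variance, its typical contribution is √0.10 × 0.216 to √0.20 × 0.216, that is 0.07–0.10 SD.

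The size is assumed throughout. Free membership, the shuttle and the individual barrier plan described under Screening may keep center effects small; at 5% of variance a center term is worth almost nothing. Nor do the documents say that each participant has one fixed center, or that it is recorded before randomization, so it cannot be taken as already available. All of this limits the center part. None of it touches the case for age and sex, which follows from the design itself.

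**Conclusion.** The point holds as a weakness of pre-specification and precision, of minor to moderate severity. The factors that define the duos, and the place where the primary outcomes arise, have no guaranteed place in the Aim 1–3 between-arm models.

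The documents do not support a claim of systematic bias, of a definite exclusion of center, or of a large loss. Under the stated assumptions, fixing age and sex is worth about 1–6 power points. A center term ranges from a slight loss (about 3%, near 5% by formula with five centers) to a gain of 12–18% if center explains a fifth of the variance. The type I error inflation for Aim 1 applies only if model-based Poisson errors are used without any allowance for extra spread, and its size depends on a between-center variance that the documents do not give.

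**What to change.** In the Data analyses section:
- Name age (in a stated form, such as linear) and sex as terms in the Aim 1, 2 and 3 between-arm models, whatever the exploration shows.
- Record each participant's expected center before each randomization. Include it as a fixed effect or random intercept, with a stated rule for pooling very small centers. Use the recorded center even if the participant later trains elsewhere.
- Use robust or overdispersion-adjusted standard errors for the Aim 1 count model.
- Label models with covariates found by exploration as sensitivity analyses.

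Leave allocation as it is, since matching on center would leave too many duos unfilled.

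The cost is a few lines of text, one added data item, and 4–6 degrees of freedom (age 1, sex 1, centers K − 1 = 2–4). If center has no effect, precision falls slightly, as shown in the table.

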After completing Aim 1 and the associated post-test, all participants who completed an average of \geq 1 exercise session per week will be eligible to continue on to Aim 2. The only difference between Aims 1 and 2 will be the financial incentive scheme; the overall exercise goals, and provision of transportation and professional oversight will remain the same. Similarly, after completing Aim 2 and the associated post-test, all participants who have averaged \geq 1 exercise session per week in Aim 2 will be eligible to continue on to Aim 3. No changes will be made to the exercise goals or availability of transportation and facilities in Aim 3.

To allow for potential schedule conflicts and missed sessions (e.g., illness, travel) participants will be allowed to "catch-up" by performing up to 3 extra sessions within the 3 weeks following a week with less than 3 sessions. Thus, if an entire week is missed due to illness, 12 sessions for payment can be completed over the next 3 weeks instead of the targeted 9 sessions. Additionally, participants will not be discouraged from performing more than the targeted exercise volume of 3 days per week of 60 minutes per session. Exercise beyond this target that is performed at school, at home or at the Wellness Centers is acceptable, since the goal of this program is to foster increased physical activity. Participants will be instructed to include such extra physical activity in their exercise log book, though they will not receive payment for days or time beyond the structured incentive program. This information will be used as part of the data analysis plan if applicable.

Post-training testing: After each of the 16-week exercise phases in Aims 1, 2, and 3, the clinical outcome tests performed at the baseline will be repeated. Staff that supervise exercise sessions will not be blinded to group assignment, but most other staff, including nurses and chemistry lab staff, will not know group assignments, so the potential for bias is expected to be low. The fasting blood sample will be acquired 2 days (38-48 hours) after the last exercise session in order to assess exercise adaptations that are distinct from the residual effects of the most recent training session. The exercise fitness and body composition tests will also be repeated at the end of each study phase.

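### Fixed, published blocks of two let anyone who knows the first member's arm deduce the second's, and the plan states no concealment before assignment

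*Combined protocol and SAP*

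**What the plan says.** The Group assignment paragraph applies one scheme to all three randomised phases: "Within each Aim, participants will be assigned to one of two groups using a randomized stratified block design". The block size is given: "Participants will be assigned to blocks of 2 (duos) matched for age and sex". An unmatched participant opens a duo ("A participant who is not yet matched on the two factors will determine the age and sex for a newly established duo"), and the next match fills it ("The next participant to meet those matching criteria will be assigned to that duo"). The two members go to different arms: "Each duo will have one participant in each of the intervention groups". The random element is the order within the duo: "the group to which each participant in a block is assigned will be pre-determined by a unique random permutation".

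Under Post-training testing the plan says "Staff that supervise exercise sessions will not be blinded to group assignment". It adds that the majority of other staff, nurses and laboratory staff among them, will not know assignments, and expects little bias as a result. The arms differ in payment (Incentive programs, Aim 1), so participants know their own.

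On covariates, Data analyses says "Since group assignments will be balanced for age and sex, the groups are expected to be similar at baseline". It then adjusts for confounders or modifiers found in initial data exploration.

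The document does not say who generates or holds the list, whether enrolling staff are kept unaware of earlier assignments, when assignment occurs relative to the Pre-test, or how close in age a match must be.

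**The concern.** A block of two has one random assignment; the other is its complement. Fixing the permutation in advance randomises the first member and does not hide the second.

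The Aim 1 primary outcome is the number of fitness center visits, and participants choose how often to attend (Exercise training), so motivation feeds directly into it. Information on motivation exists before assignment, because screening includes an interview about barriers and a motivation questionnaire. Eligibility also includes a judgement about willingness to complete the schedule. The Design paragraph has 105 enrolled and 80-90 entering the programme. If assignment comes before or during that loss, a known arm could affect who starts. If the person enrolling knew the open slot, a difference in motivation between arms could pass for an incentive effect.

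The covariate rule is a separate, smaller matter. Age and sex are balanced by design, so a search for differences between arms will tend to pass over them. The analysis would then ignore the factors used to form the duos.

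**Working it through.** The plan gives no figure for predictability, power or expected imbalance, so there is nothing of its own to reproduce.

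**Inputs.** N = 86, a working value within the stated 80-90. Both sexes and ages 11-21 give 11 × 2 = 22 cells if ages match by whole year. Coarser matching is represented by 4 and 10 cells. The cell counts, and equal cell sizes, are assumptions.

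**1. Assignments that follow with certainty under duos.** One assignment per completed duo is certain. With S equal cells, the expected number of cells left with an unfilled duo is U = (S/2) × [1 − (1 − 2/S)^N]. The expected number of certain assignments is (N − U)/2.
- S = 22: U = 11.0; (86 − 11)/2 = 37.5; 37.5/86 = 44%.
- S = 10: U = 5.0; (86 − 5)/2 = 40.5; 40.5/86 = 47%.
- S = 4: U = 2.0; (86 − 2)/2 = 42; 42/86 = 49%.
- Ends of the stated range at S = 22: 34.5/80 = 43% and 39.5/90 = 44%.

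First members, and members of unfilled duos, are not predictable.

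**2. Best-guess accuracy under duos.** Certain assignments are guessed correctly and the rest half the time: 0.5 + 0.5 × share. This gives 72% for 22 cells and 74% for 4.

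**3. Random blocks of 2 and 4.** Assume equal chances of each size, and an observer who knows the possible sizes but not which is in use. Certainty arises only when a block of 4 opens with two like assignments, which has probability 1/3. The third and fourth slots are then both certain. In long cells the rate is (1/2 × 1/3 × 2) / 3 = 1/9, or 11%, where 3 is the mean block length. Incomplete blocks at the end of each cell lower it. Simulation at N = 86:

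| Cells | Certain | Best guess correct |
|---|---|---|
| 22 | 7% | 68% |
| 10 | 9% | 70% |
| 4 | 10% | 71-72% |

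Varying the block size removes most of the certainty but little of the guessability.

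**4. Cost in balance, 22 cells.** With duos the mean absolute difference in arm totals is about √(2 × 11/π) = 2.6. Simulations give 2.5-2.7 for duos and 3.1-3.3 for random 2/4 blocks, a loss of about 0.6 of a participant.

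**5. Illustrative bias, on assumed inputs only.** Bias in SD units = predictable share × fraction steered × gap between candidates.
- 0.5 × 0.25 × 0.5 = 0.06 SD.
- 0.5 × 0.5 × 1 = 0.25 SD.

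With SE = √(4/N), a bias of 0.25 SD would turn a nominal two-sided 5% error into 20% (N = 80) to 22% (N = 90). The document supplies neither the fraction steered nor the gap.

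**6. Omitted matching factors.** In a linear model, matching on prognostic factors lowers the true variance of the arm difference. Leaving those factors out puts their variance back into the residual, so the reported standard error is generally too large.

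**The case against.** **Who knows the first arm.** The deduction needs someone who is told the first member's arm and can influence the next entry. Only exercise supervisors are stated to be unblinded. They are fitness center professionals, and nothing gives them a recruiting role; screening and consent are described separately. A reader might infer that enrolling staff can see which duo is open, or that enrolment was steered. The document supports neither. This objection stands, and it makes the point one about an unstated safeguard. It does not close the point, because enrolling staff are not named among those unaware of assignments, and the low-bias remark belongs to post-training testing, not to concealment beforehand.

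**How much room there is to steer.** The plan assigns the next matching participant, so steering means delaying or discouraging someone, or having two matching candidates at once. With 22 cells there are about 86/22 = 3.9 participants per cell. If accrual took 12 to 36 months (assumed), the chance of another same-cell entrant in a given month is 1 − exp(−3.9/12) = 28% down to 1 − exp(−3.9/36) = 10%. With 4 cells it is 83% down to 45%. Opportunity therefore depends on the unstated match tolerance.

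**Aims 2 and 3.** A reader might carry the full concern into the later phases. There is no recruitment pool there: entry follows a completed phase, its post-test and a recorded average of at least one session per week. Only the order of re-randomisation could be influenced, although attendance histories are by then known.

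**Block size as the cure.** Varying the blocks might be thought almost to abolish predictability. Counting only the third slot after two like assignments would suggest 4-5% certain, but the fourth slot is then certain too, and guessing barely worsens.

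**Covariates.** Age and sex are not excluded, merely not guaranteed. A reader might fear false positives from leaving them out; in a linear model the error generally runs the conservative way.

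**Conclusion.** The point holds as a gap in protection against selection bias. The deducible share, 44% to 49% at N = 86, follows from the protocol's own rule; its position in that range rests on the assumed age-sex cells. Whether anyone could use it is unknown, because concealment before assignment is not described. There is no evidence of steering, and no bias in SD units can be attributed to this trial: the 0.06 and 0.25 SD figures only illustrate sensitivity. The exposure is greatest in Aim 1 and is confined to ordering in Aims 2 and 3. The covariate matter concerns precision in the linear models, and no claim is made here about the direction of the effect in the Aim 1 Poisson model. The change is worth making because it is cheap, not because the result is shown to be wrong.

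**What to change.** 1. **Conceal the list (main step).** Name someone on the existing team, outside recruitment, to hold it. Release each assignment only after eligibility and the Pre-test, or the preceding Post-test for Aims 2 and 3, are complete and logged. Duos could remain if this is in place.
2. **Vary the blocks (secondary).** Define the age-sex strata, including the age bands, and use undisclosed random blocks of 2 and 4 within them. The price is the slightly looser balance shown above, which the covariates in step 3 largely absorb.
3. **Fit age and sex in every between-arm model**, whatever the observed balance, and say so in Data analyses.

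The cost is a short amendment, a new allocation list and a small logging task. No extra participants or visits are needed.
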